5.1.3 Evaluation of Disease in Lymph Nodes and Viscera

5.1.3.1 Baseline Tumor Assessments

The baseline tumor burden will be assessed by CT of the neck, chest, abdomen and pelvis within 30 days prior to the first dose of study drug. The Investigator will identify, prospectively, the lesions to be followed to evaluate the subject's response to therapy.

5.1.3.2 Method of Tumor Response Assessment

The same method of assessment and the same technique should be used to characterize each identified and reported lesion at Screening and at reassessment during treatment. Imaging-based evaluation is preferred to evaluation by clinical examination when both methods have been used to assess the anti-tumor effect of a treatment. Lesions evaluated clinically will only be considered measurable when they are superficial (e.g., skin nodules, palpable lymph nodes).

Central review of radiologic images may be performed to confirm the date of disease progression.

5.1.3.3 Determination of Response in Lymph Nodes and Viscera

The Investigator will make a determination of response based on criteria as specified in the protocol. In subjects with lymph node and/or visceral involvement, responses (CR and PR) must be confirmed for a minimum of 4 weeks.

5.1.4 Global Composite Response Score

Overall response will be based on response in each compartment (skin, blood, lymph nodes and viscera) as specified in the protocol. Node, viscera and blood response contributes towards global response only if disease was present at baseline, unless defining global PD which is met by new disease in a previously uninvolved compartment.

Subjects who meet PD criteria in any compartment, or relapse in blood, lymph nodes or viscera, confirmed at two consecutive visits must be discontinued from study treatment due to disease progression/relapse. If subsequent assessment does not confirm PD in any compartment, or relapse in blood, lymph nodes or viscera, subject may continue on treatment. An unconfirmed PD/relapse would not preclude future responses (CR or PR).

If PD is documented in any compartment at any point leading to subject's discontinuation from treatment, the overall global composite score should be completed at that time even if all compartments have not been assessed.

5.1.4.1 Independent Review of Progression

A blinded Independent Review of response data for each subject will be performed to make a determination regarding progression and the date of progression. The nodal and visceral compartments evaluation will be based upon radiologic data. The independent radiology review of radiographic exams will provide an assessment of tumor response and progression for all subjects. A separate radiology charter will detail the roles and responsibilities of the radiology reviewers and how the reads will be performed. An independent reviewer (IR) will assess PFS based on date of progression or death, whichever comes first. For this assessment the independent reviewer will be supplied the results of the independent radiology review, the mSWAT score for each subject, as assessed by the investigator, and the results of central flow cytometry in order to assess blood response, and date of death for subjects who died before progression.

Secondarily, the IR will review the date of any objective responses (CR or PR) for each subject.

The independent review charter identifies the data package that the Independent Reviewer receives to review responses for each subject with baseline and at least on post-baseline measurement in the study.

5.2 Safety Assessments

The safety of KW-0761 and vorinostat will be determined by reported AEs, changes in physical examinations, vital sign measurements, electrocardiograms (ECGs) and laboratory analyses. Safety evaluations will be performed throughout the study. All subjects who received at least one dose, including a partial dose, of study drug will be evaluated for safety.

5.2.1 Adverse Events

All subjects will be assessed regularly for potential occurrence of AEs from the time of signing the informed consent until 90 days after the last dose or initiation of alternative therapy whichever comes first. In all subjects who cross over from vorinostat to KW-0761, the causality of any reported AEs should be assessed for both drugs for 30 days after vorinostat was stopped (or later if the event is considered to be related to vorinostat).

All AEs will be coded by Medical Dictionary for Regulatory Activities (MedDRA, version 15.1). The National Cancer Institute-Common Terminology Criteria for Adverse Events (NCI-CTCAE) v4.0 system will be used to grade AEs, both clinical and laboratory.

5.2.2 Clinical Laboratory Evaluations

Clinical laboratory assessments will be performed at the visits specified in the Study Procedures tables of the protocol. A pregnancy test (serum or urine) is to be performed for all women of childbearing potential prior to administration of study medication.

Clinical laboratory assessments are specified in the protocol.

5.2.3 Vital Signs and Body Weight

Vital signs (pulse, respiration rate, temperature, and blood pressure) will be measured, with the subject in the seated position, at the visits specified in the Study Procedures tables of the protocol. Additional vital signs will be obtained if clinically significant signs or symptoms occur.

Weight will be included in vital sign assessments.

5.2.4 Physical Examination

The Investigator will perform a full physical examination at the Pre-treatment (including height at only this visit) and End of Treatment visits and brief physical examinations at other visits specified in the Study Procedures Tables in the protocol.

Eastern Cooperative Oncology Group (ECOG) Performance Status (PS) will be assessed at each exam according to the ECOG PS criteria.⁴

5.2.5 Electrocardiograms

A baseline 12-lead ECG is to be obtained at the Pre-treatment Visit. Follow up ECGs should be performed during the study if clinically indicated and then at the End of Treatment visit.

The Investigator will have the responsibility for evaluating the ECG interpretation in relationship to clinical signs and symptoms and for reaching a medical decision regarding the subject's medical status. If not within normal limits, the ECG findings should be marked "clinically significant" or "not clinically significant" (i.e., "CS" or "NCS") and the ECG should be initialed and dated by the Investigator.

5.2.6 Blood Sample for Determination of Natural Ligands

Blood samples will be drawn to measure the concentration of natural ligands such as CCL17/TARC and CCL22/MDC at the visits specified in the Study Procedures Tables in the protocol. Analysis of samples will be performed by a central laboratory designated by the Sponsor.

5.2.7 Genomic Sampling (For subjects receiving KW-0761 as first assigned therapy only)

A saliva sample will be collected to obtain baseline germline DNA sample to assess Fc-gamma receptor polymorphisms. Exploratory analysis of the effect of this genetic determinant on safety parameters may be performed. Analysis of samples will be performed by a central laboratory designated by the Sponsor.

5.2.8 Immunogenicity (For subjects receiving KW-0761)

Serum samples will be drawn for the determination of anti-KW-0761 antibodies and concentration of KW-0761 at the visits specified in the Study Procedures Tables in the protocol. Analysis of samples will be performed by a central laboratory designated by the Sponsor.

5.3 Pharmacokinetic Assessments

Serum samples will be drawn in subjects who receive KW-0761 (as first assigned therapy or crossover) at the timepoints specified in the Study Procedures Tables in the protocol for

determination of KW-0761 concentration, through Cycle 3 and at the End-of-Treatment Visit. At selected sites, 4 additional samples will be drawn between 6 and 8 hours, and at 24, 48, and 72 - 96 hours after the first infusion on Day 1/Cycle 1 in approximately 10 subjects. All samples will be sent to a central laboratory designated by the Sponsor.

5.4 Quality of Life Assessments

Subjects with CTCL often suffer from the symptoms related to their disease (pain, sleep disturbance, etc.), the social and psychological problems related to sometimes unsightly skin lesions and the burden of living with a chronic disease. In an effort to assess some of these QoL issues, the Skindex-29, FACT-G, and EQ-5D-3L will be administered.

5.5 Follow-Up

- All subjects will be contacted by telephone every 30 days (+/- 7 days) up to 90 days after the last dose of study medication or initiation of alternative therapy, whichever comes first, to confirm any new onset AEs or toxicities. In all subjects who cross over from vorinostat to KW-0761, the causality should be assessed for both drugs for 30 days after vorinostat was stopped (or later if the event is considered to be related to vorinostat).
- After a subject who receives KW-0761 goes off study, if CD4 and CD8 counts are less than $200/\text{mm}^3$ at the End-of-treatment visit, they will be followed every 3 months (+/- 14 days) until they return to at least $200/\text{mm}^3$, initiation of alternative therapy, or 1 year, whichever comes first.
- In the absence of disease progression, all subjects or their referring physicians will be contacted every 3 months (+/- 14 days) until documented disease progression or death, or initiation of alternative therapy.
- All subjects or their referring physician will be contacted every 3 months (+/- 14 days) to ascertain survival status.
- All follow up information and attempts to obtain follow up information should be documented in the subject's source record.

5.6 Follow-Up for Subjects Achieving a Complete Response

Those subjects who do not continue treatment after achieving a CR will undergo the following assessments every 8 weeks (+/- 14 days) for the first 6 months (if CR achieved prior to one year on study) and then every 16 weeks (+/- 14 days) thereafter until progression:

- Chemistry/Hematology profile;
- Skin photographs;
- mSWAT;
- Pruritus evaluation;

- Blood sample for flow cytometric analysis;
- CT;
- Overall Disease Response;
- Immunogenicity (for subjects receiving KW-0761).

6 STATISTICAL METHODOLOGY

6.1 General Statistical Consideration

Summary statistics will be presented by treatment arm. For continuous variables, the number of available observations (n), mean, standard deviation (SD), median, minimum, and maximum will be provided. For categorical variables, the frequency and percentage in each category will be displayed. Additionally, the point estimates will be accompanied by the corresponding 2-sided 95% confidence intervals.

For summary statistics, the mean and median will be displayed to one decimal place greater than the original value and the measure of variability (e.g., standard deviation) will be displayed to two decimal places greater than the original value.

Unless otherwise specified, all efficacy and safety analyses will be performed based on the first assigned therapy. For those subjects in the vorinostat arm who cross over into the KW-0761 arm, efficacy and safety data collected during the crossover portion will be presented separately within the KW-0761 crossover group.

All analyses will be performed using SAS[®] Version 9.3 or higher.

6.2 Baseline Definition

For analyses of study variables based on the first assigned therapy, baseline is defined as the last measurement obtained prior to the first dose of study drug. For analyses of study variables in the crossover portion, baseline is defined as the last measurement obtained prior to the first dose of KW-0761.

6.3 Determination of Sample Size

Since the primary endpoint is PFS, the reference median PFS for vorinostat is assumed to be 169 days.⁵ The median PFS for KW-0761 therapy is targeted for 254 days, a 50% improvement over this reference median. For a 24-month accrual and 12 month follow-up on the last subject dosed, Table 10.3-1 of the protocol gives the power and the number of PFS events required to show superior PFS for KW-0761 therapy over vorinostat at the one-sided

0.025 significance level. The Intent-to-Treat (ITT) set is used for this primary analysis. The same analysis conducted using the Efficacy Evaluable set is considered secondary.

Under these assumptions, for the ITT population, a total of 255 PFS events will give 90% power. For this study, the final primary analysis comparing PFS between treatment groups will not be conducted until 255 PFS events occur or until a maximum of 24 months after the last randomized subject's first dose, whichever comes first. In the event that the study is stopped prior to 255 PFS events being observed, the primary test will be performed at less than 90% power under the current assumptions according to Table 10.3-1 in the protocol.

Each of these calculations used a log-rank test to compare the two survival curves. Sample size calculations were computed using SAS software version 9.3 using PROC POWER, Twosamplesurvival test = logrank.

The total sample size of 288 represents the approximate number of subjects that may be necessary for 255 PFS events to occur within the projected 36 months of the trial. If a 10% inflation factor is applied to this total (about 29 subjects) to take into account those subjects that may be lost to follow-up prior to documented progression, a total of 317 enrolled subjects may be necessary in order to observe 255 PFS events.

The observed rates of PFS events, recruitment, and drop-outs will be monitored throughout the study and may be used to alter the number of sites, the accrual period, and the follow-up period to achieve the required 255 PFS events in a timely manner. If the 255 PFS events are not observed within 36 months from the start of enrollment the study will be stopped at approximately 24 months after the last randomized subject's first dose.

6.4 Analysis Sets

- Intent-to-Treat (ITT) Set: Includes all subjects randomized to a therapy (KW-0761 or vorinostat) and assigned a study number.
- Safety Analysis Set: Includes all subjects who received at least one dose (even a partial dose) of the assigned study agent (KW-0761 or vorinostat).
- Efficacy Evaluable Set: Includes all subjects who receive the first cycle of treatment (at least one dose) and who have baseline tumor assessment and at least one post-baseline assessment for response. If a subject had baseline tumor assessment but progressed (died before progression or had documented progression in follow-up period) during the study without any post-baseline tumor assessment, that subject will still be considered as efficacy evaluable.
- Pharmacokinetic (PK) Analysis Set: All subjects who provide at least one post-dose KW-0761 concentration measurement will be included in the PK analysis set.

6.5 Interim Analysis and Data Monitoring

No formal interim analysis is planned for this study.

A Data Safety Monitoring Board (DSMB) will be responsible for overseeing subject safety in the trial. The DSMB will be comprised of at least two medical doctors and a statistician. A detailed DSMB charter will be developed prior to the safety review.

6.6 Subject Disposition

Subject disposition will be summarized for each treatment arm and in total for all randomized subjects. The following subject disposition categories will be included:

- Subjects who were randomized;
- Subjects who were randomized and did not receive any assigned study drug;
- Subjects who were randomized and treated;
- Subjects who discontinued randomized study drug; and
- Subjects who discontinued from the study.

For subjects who discontinued randomized study drug and subjects who discontinued from the study, a summary of reasons for discontinuation will be provided. The number of subjects in the ITT, Safety Analysis and Efficacy Evaluable Sets will also be summarized.

For subjects who were randomized to vorinostat arm but then cross over into KW-0761 arm, the following disposition categories will be presented for the crossover portion:

- Subjects who were randomized to vorinostat and crossed over to KW-0761;
- Subjects who were crossed over to KW-0761 but did not receive KW-0761;
- Subjects who were crossed over to KW-0761 and received KW-0761;
- Subjects who were crossed over to KW-0761 and discontinued KW-0761; and
- Subjects who were crossed over to KW-0761 and discontinued from the study.

The reasons for discontinuation of KW-0761 and discontinuation from the study during the crossover portion will be provided.

All disposition data will be listed by subject corresponding to their first assigned therapy. A listing will be provided that indicates each subject's inclusion/exclusion from the analysis set and the reason(s) for exclusion from the Efficacy Evaluable Set.

6.7 Demographic and Baseline Disease Characteristics

Demographic and baseline characteristics will be summarized descriptively for the ITT Set, Safety Analysis Set, and the Efficacy Evaluable Set by treatment arm and in total. Gender, race, ethnicity, region, and baseline ECOG performance status will be summarized with contingency tables. Age at screening (years), height, weight, body surface area (BSA), and body mass index (BMI) at baseline will be described with summary statistics (n, mean, standard deviation, median, minimum, and maximum).

Baseline disease characteristics will be collected at screening and will be summarized descriptively for each treatment arm and in total. Time from initial diagnosis (months) will be summarized with descriptive statistics (n, mean, standard deviation, median, minimum, and maximum). Histologically confirmed diagnosis type (MF or SS), clinical stage at diagnosis, current clinical stage, current sites of disease, CCR4 expression status, number of prior CTCL therapies, best response to the last CTCL therapy prior to study entry, and prior radiotherapy will be summarized to show the number and percentage of subjects in each category.

All demographic data and baseline disease characteristics data will be listed by subject.

6.8 Medical and Surgical History

Medical/surgical history will be listed by subject.

6.9 Prior/Concomitant Medications

Prior and concomitant medications will be coded using the World Health Organization (WHO) Drug Dictionary (September 2012). Prior medications include medications that were taken within 30 days prior to study entry and stopped prior to start of randomized treatment. Concomitant medications during the randomized treatment period include medications that started at any time and were taken at any time after the start of treatment until the end of the entire randomized treatment period.

The number and percentage of subjects taking concomitant medications during randomized treatment period (excluding crossover) will be summarized by anatomical therapeutic chemical (ATC) and preferred term (PT) for the Safety Analysis Set. Although a subject may have taken two or more medications, the subject is counted only once within an ATC classification. The same subject may contribute to two or more preferred terms in the same classification.

All prior and concomitant medications will be listed by subject. Pruritus medications will also be listed.

6.10 Study Drug Exposure and Compliance

Extent of exposure in days for each subject for the entire randomized treatment period will be calculated as the last dose date of study drug (KW-0761 or vorinostat) minus the first dose date of study drug plus 1. Extent of exposure and total number of cycles initiated during the randomized treatment period will be summarized using descriptive statistics by treatment arm and in total for the Safety Analysis Set. The number and percentage of subjects who initiated treatment for at least 1, 2, 3, 4, 5, and 6 or more cycles will be tabulated by treatment arm and in total.

For the KW-0761 arm, the number of KW-0761 infusions administered, the planned dose (average of the planned dose per subject), the actual dose (average of the actual dose received per subject), and the % dose intensity (total actual dose/total duration of treatment/7) / (total planned dose/total planned weeks) of KW-0761 will be calculated and summarized descriptively. Total planned weeks are based on a 28 day cycle. The following categories of KW-0761 dosing status will be summarized:

- Subjects with total planned dose not administered;
- Subjects with a dose withheld for KW-0761; and
- Subjects with a KW-0761 infusion temporarily interrupted.

In addition, the reasons will be provided for subjects with total planned dose of KW-0761 not administered and for subjects with KW-0761 infusion temporarily interrupted.

For the vorinostat arm, the number and percentage of subjects with dose modifications and the number and percentage of subjects who had non-compliance with dosing for vorinostat will be provided.

For subjects who were randomized to vorinostat arm but then cross over into KW-0761 arm, the extent of exposure to KW-0761 and the total number of cycles initiated during the crossover portion will be summarized. In addition, the number of KW-0761 infusions administered, the % dose intensity, and the dosing status of KW-0761 during the crossover portion will also be summarized descriptively.

All study drug administration data will be listed by subject.

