3.2.2.1 Study Drug: KW-0761 (mogamulizumab)

Treatment can be administered on an outpatient basis. Subjects will receive 1.0 mg/kg of KW-0761 as an intravenous (iv) infusion over at least 1 hour on Days 1, 8, 15 and 22 of the first cycle and on Days 1 and 15 of subsequent cycles. Each treatment cycle is 28 days.

No dose modifications of the KW-0761 will be permitted in this study. Subjects will not be replaced.

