Demographic and Baseline Disease Characteristics
Safety Analysis Set

Table 14.1.2.3
Demographic and Baseline Disease Characteristics
Efficacy Evaluable Set

Table 14.1.3
 Summary of Concomitant Medications During Randomized Treatment Period - Number (%) of Subjects
 Safety Analysis Set

ATC Classification Preferred Term	Vorinostat N=xxx		KW-0761 N=xxx	
	n	(%)	n	(%)
Total	xx	(xx.x)	xx	(xx.x)
ATC Classification 1	xx	(xx.x)	xx	(xx.x)
Preferred Term 1	xx	(xx.x)	xx	(xx.x)
Preferred Term 2	xx	(xx.x)	xx	(xx.x)
Preferred Term 3	xx	(xx.x)	xx	(xx.x)
ATC Classification 1	xx	(xx.x)	xx	(xx.x)
Preferred Term 1	xx	(xx.x)	xx	(xx.x)
Preferred Term 2	xx	(xx.x)	xx	(xx.x)
Preferred Term 3	xx	(xx.x)	xx	(xx.x)

Note: Percentage is calculated using the number of subjects in the column heading as the denominator. Medications that started at any time and were taken at any time after the start of treatment until the end of the entire randomized treatment period are included.

Table 14.1.4
 Summary of Extent of Exposure to Randomized Study Drug
 Safety Analysis Set

	Vorinostat N=xxx	KW-0761 N=xxx
Extent of Exposure (Days)		
n	xx	xx
Mean	xx.x	xx.x
Std Dev	xx.xx	xx.xx
Median	xx.x	xx.x
Minimum	xx	xx
Maximum	xx	xx
Number of KW-0761 Infusions Administered		
n		xx
Mean		xx.x
Std Dev		xx.xx
Median		xx.x
Minimum		xx
Maximum		xx
Total Number of Cycles Initiated		
n	xx	xx
Mean	xx.x	xx.x
Std Dev	xx.xx	xx.xx
Median	xx.x	xx.x
Minimum	xx	xx
Maximum	xx	xx
Subjects Who Initiated Treatment for at Least*		
1 Cycle	xx (xx.x)	xx (xx.x)
2 Cycles	xx (xx.x)	xx (xx.x)
3 Cycles	xx (xx.x)	xx (xx.x)
4 Cycles	xx (xx.x)	xx (xx.x)
5 Cycles	xx (xx.x)	xx (xx.x)
6 Cycles	xx (xx.x)	xx (xx.x)
Etc.		

Note: Percentage is calculated using the number of subjects in the column heading as the denominator.

* A subject is considered initiated treatment for a cycle if the subject received any assigned study drug for that cycle.

** % dose intensity is calculated as $100 * (\text{total actual dose} / \text{total duration of treatment} / 7) / (\text{total planned dose} / \text{total planned weeks})$.

Table 14.1.4
 Summary of Extent of Exposure to Randomized Study Drug
 Safety Analysis Set

	Vorinostat N=xx	KW-0761 N=xx
Average Planned Dose of KW-0761 (mg)		
n		xx
Mean		xx.x
Std Dev		xx.xx
Median		xx.x
Minimum		xx
Maximum		xx
Average Actual Dose of KW-0761 (mg)		
n		xx
Mean		xx.x
Std Dev		xx.xx
Median		xx.x
Minimum		xx
Maximum		xx
% Dose Intensity of KW-0761**		
n		xx
Mean		xx.x
Std Dev		xx.xx
Median		xx.x
Minimum		xx

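### As written, the KW-0761 % dose intensity formula scores a fully dosed subject at about 2%, and the treatment duration it uses is never defined

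*SAP*

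**What the plan says.** SAP 6.10 (Study Drug Exposure and Compliance) plans a descriptive summary of % dose intensity for the KW-0761 arm, and again for subjects who cross over from vorinostat. The formula is "total actual dose/total duration of treatment/7) / (total planned dose/total planned weeks". The footnote to the Table 14.1.4 shell, introduced by "dose intensity is calculated as", repeats the expression with a factor of 100 and the same placement of the 7. Table 14.1.6 (crossover) is to follow that layout.

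The same section measures "Extent of exposure in days for each subject" as "the last dose date of study drug (KW-0761 or vorinostat) minus the first dose date of study drug plus 1". On the planned side, "Total planned weeks are based on a 28 day cycle". SAP 3.2.2.1 schedules infusions "on Days 1, 8, 15 and 22 of the first cycle and on Days 1 and 15 of subsequent cycles" and adds that "Each treatment cycle is 28 days".

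Neither document defines total duration of treatment, the term the formula uses. Extent of exposure is the only treatment length defined in 6.10.

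**The concern.** The denominator of the formula is planned dose per week, so the numerator must also be dose per week. With exposure in days, the 7 can only be meant to turn days into weeks. Read left to right, it divides the dose rate instead of the duration.

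There is a second question behind the first. If duration stops on the day of the last infusion while planned weeks run to the end of the cycle, the time after the last infusion counts on one side only.

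The SAP states that "No dose modifications of the KW-0761 will be permitted in this study". Shortfalls in delivery therefore come from skipped, delayed, withheld or incomplete infusions rather than reduced doses. Dose intensity is the planned summary that sets the dose delivered against time. A value near 2% would be noticed. A value of 108% looks plausible and could stand in the exposure tables while hiding a missed infusion.

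**Working it through.** The plan states no numerical dose intensity, so there is no figure to reproduce. The test case is a subject who receives every planned dose in full and on schedule, who should score 100%.

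**Inputs**
- A = total actual dose and P = total planned dose, with A = P for full dosing. Infusions are treated as equal in size, which assumes constant weight.
- W = total planned weeks = 4c for c cycles of 28 days (SAP 6.10, 3.2.2.1). Assumption: whole cycles are counted.
- D = duration in days. Assumption: D is the extent of exposure in 6.10. The last infusion is on Day 22 if only Cycle 1 is given, otherwise on Day 15 of the last cycle. So D = 22 for c = 1 and D = 28(c - 1) + 15 for c of 2 or more.

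**Formulas with A = P**
- As written: 100 x (A/D/7) / (P/W) = 100W/(7D).
- With the duration divided by 7: 100 x [A/(D/7)] / (P/W) = 700W/D.
- The second is 7 x 7 = 49 times the first, whatever D is.

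| Cycles | D (days) | W (weeks) | As written | Bracketed |
|---|---|---|---|---|
| 1 | 22 | 4 | 2.60% | 127.3% |
| 2 | 43 | 8 | 2.66% | 130.2% |
| 6 | 155 | 24 | 2.21% | 108.4% |
| 12 | 323 | 48 | 2.12% | 104.0% |
| 24 | 659 | 96 | 2.08% | 102.0% |

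Example for 1 cycle: as written, 100 x 4/(7 x 22) = 2.60%; bracketed, 700 x 4/22 = 127.3%.

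**Other readings of D**
- D in weeks, formula as written: 100W/D, with D now in weeks, loses its meaning once the result is divided by 7 again. It gives 18.2% at 1 cycle and 14.9% at 12, so this reading does not rescue the formula.
- D as whole cycles (28c days): as written, 100 x 4c/(7 x 28c) = 100/49 = 2.04%; bracketed, 700 x 4c/(28c) = 100.0%.
- Last infusion moved by 2 days either way, D as extent of exposure, bracketed: 117% to 140% at 1 cycle, 124% to 137% at 2, 103% to 105% at 12.

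**Can a missed dose be hidden?** Bracketed, D as extent of exposure, one infusion missed other than the last. Planned infusions number 4 + 2(c - 1).
- 2 cycles: 5/6 x 56/43 = 108.5%.
- 3 cycles (D = 71): 7/8 x 84/71 = 103.5%.
- 6 cycles: 13/14 x 168/155 = 100.6%.

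**Does the choice of end point matter?** Take a subject who stops after Day 1 of Cycle 3, with 7 of 8 planned infusions and 12 planned weeks.
- Duration to the end of the 14-day interval after the last infusion (10 weeks): (7/10)/(8/12) = 105%.
- Duration to the end of the started cycle (12 weeks): (7/12)/(8/12) = 87.5%.

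Only the second uses one window on both sides.

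**The case against.** The misplaced 7 is a notation slip whose intent is clear, and a table showing fully dosed subjects near 2% would be caught in programming. That is likely. Even so, the text is wrong in two places and nothing elsewhere in the SAP corrects it.

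The stronger objection concerns the second part. A reader might infer that the SAP ends the duration at the last dose, so that both the literal and the bracketed formula must be wrong. The documents do not establish this. Total duration of treatment and extent of exposure are different terms, and the link between them is an inference. If duration means whole cycles, bracketing alone gives exactly 100%. What stands is that the term is undefined and that the only treatment length 6.10 defines leads to values above 100%.

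Two further inferences go too far. One is that dose intensity is the sole measure of delivery: 6.10 also plans the number of infusions, planned and actual doses, and counts of withheld, incomplete and interrupted infusions. The other is that the by-subject data are affected. Listing 16.2.5.1 has a % dose intensity column beside each infusion but gives no formula, so the documents do not show that the cumulative expression is used there.

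**Conclusion.** The formula is wrong as written in SAP 6.10 and in the Table 14.1.4 footnote. With duration in days it is 49 times too small, and full dosing scores between 2.0% and 2.7% instead of 100%. This does not depend on whether duration ends at the last dose or at the end of the cycle.

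The second part is conditional. It rests on reading duration as extent of exposure and planned weeks as whole cycles. Under that reading the bracketed formula overstates full dosing most for short treatment (127% and 130% at 1 and 2 cycles) and least for long treatment (102% at 24). Subjects treated for different lengths of time would not be comparable, and one missed infusion could still score above 100%.

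The consequence is confined to descriptive exposure summaries for the randomized KW-0761 arm and the crossover portion. The PFS test, its alpha and its power are untouched. It should be corrected because it is an error in a stated rule and cheap to mend.

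**What to change.** In SAP 6.10 and the Table 14.1.4 footnote, write:

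% dose intensity = 100 x [total actual dose / (duration in days / 7)] / [total planned dose / total planned weeks].

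Define duration explicitly, and use one and the same window for duration, planned dose and planned weeks, for example 28 days times the number of cycles initiated. Apply the same definition to the crossover summary in Table 14.1.6. Full dosing then scores exactly 100%.

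The sponsor should know one property of that example: the two time terms cancel, so the measure becomes actual over planned dose and a delayed cycle start no longer lowers it. If delays are meant to count, the definition of duration should say so.

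The cost is one formula, one definition and one table footnote. No data collection or trial procedure changes.
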